11.2. Definitions

11.2.1. Adverse Event (AE)

An adverse event is any undesirable sign, symptom or medical condition or experience that develops or worsens in severity after starting the first dose of study treatment or any procedure specified in the protocol, even if the event is not considered to be related to the study.

Abnormal laboratory values or diagnostic test results constitute adverse events only if they induce clinical signs or symptoms or require treatment or further diagnostic tests.

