5.3. Definition of Dose-Limiting Toxicity

Toxicity assessments will be done using NCI Common Terminology Criteria for Adverse Events (CTCAE v4.0). CTCAE v4.0 is identified and located on the CTEP website at (http://ctep.cancer.gov/protocolDevelopment/electronic_applications/ctc.htm). Dose-limiting toxicity (DLT) refers to toxicities experienced during the first cycle of treatment. A DLT is defined as any of the following:

- **Non-Hematologic Toxicity**
 - Grade 3 or 4 events, excluding
 - Grade 3 fatigue
 - Grade 3 hypertension controlled with anti-hypertensive therapy.
 - Grade 3 hypophosphatemia
 - Grade 3 hyponatremia
- **Hematologic Toxicity**
 - Grade 4 neutropenia of ≥ 4 days duration
 - Grade 4 neutropenia of any duration with fever or documented infection
 - All other hematologic toxicities of Grade 4
 - Inability to take 75% or more of the planned dose in Cycle 1 due to treatment-related AEs

Management and dose modifications associated with the above adverse events are outlined in Section 6 (Expected Toxicities and Dosing Delays/Dose Modifications).

Dose escalation will proceed within each cohort according to the following scheme.

Number of Participants with DLT at a Given Dose Level	Escalation Decision Rule
0 out of 3	Enter 3 participants at the next dose level.
≥ 2	Dose escalation will be stopped. This dose level will be declared the maximally administered dose (highest dose administered). Three (3) additional participants will be entered at the next lowest dose level if only 3 participants were treated previously at that dose.
1 out of 3	Enter at least 3 more participants at this dose level. 
 • If 0 of these 3 participants experience DLT, proceed to the next dose level. • If 1 or more of this group suffer DLT, then dose escalation is stopped, and this dose is declared the maximally administered dose. Three (3) additional participants will be entered at the next lowest dose level if only 3 participants were treated previously at that dose.
≤ 1 out of 6 at highest dose level below the maximally administered dose	This is generally the recommended phase II dose. At least 6 participants must be entered at the recommended phase II dose.

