5.4. General Concomitant Medication and Supportive Care Guidelines

The use of any natural/herbal products or other “folk remedies” are not allowed on study. All medications must be recorded in the case report form and be reviewed by the treating physician at each visit.

Cediranib demonstrated minimal inhibitor effects on the activity of CYP3A4 (testosterone and midazolam) in vitro, although the IC50 was far in excess of the clinically relevant

concentrations. Based on in vitro and clinical exposure data, olaparib is considered unlikely to cause clinically significant drug interactions through inhibition or induction of cytochrome P450 enzyme activity. However, in vitro data have also shown that the principal enzyme responsible for the formation of the 3 main metabolites of olaparib is CYP3A4. Given this data, potent inhibitors or inducers of CYP3A4 (as outlined in Appendix D) must not be used during this study for patients receiving olaparib. Dihydropyridine calcium-channel blockers are allowed for management of hypertension.

Patient should receive general concomitant and supportive care medications based on best medical practice. Neupogen and other bone marrow-supportive agents, including erythropoiesis-stimulating agents, are not allowed during treatment.

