Absolute neutrophil count \geq 1000/mcL AND Platelets \geq 75,000/mcL AND Hemoglobin \geq 8 mg/dL	Maintain dose level
Absolute neutrophil count < 1000/mcL OR Platelets < 75,000/mcL OR Hemoglobin < 8 mg/dL	Hold treatment for up to 14 days until absolute neutrophil count \geq 1000/mcL, platelets \geq 75,000/mcL, and hemoglobin \geq 8 mg/dL. Treatment may be restarted at one dose level lower for the drug(s) causing the toxicity, as per the dose reduction levels in Sections 6.2.1 and 6.2.2, at the treating investigator's discretion. The overall PI of the study should be informed regarding all dose modifications. Patients whose counts have not recovered to absolute neutrophil count \geq 1000/mcL, platelets \geq 75,000/mcL, and hemoglobin \geq 8 mg/dL after 14 days should be removed from study.
Grade 4 hematologic AE related to cediranib or olaparib that does not resolve to absolute neutrophil count \geq 1000/mcL, platelets \geq 75,000/mcL, and hemoglobin \geq 8 mg/dL despite maximum supportive care after 14 days.	Remove patient from study.

For AEs that are unrelated to the study drugs, study drug may be held for up to 14 days at the discretion of the treating investigator. Drug holds of greater than 14 days for unrelated AEs where the patient is experiencing ongoing clinical benefit may be considered after discussion with the overall PI.

Patients in the dual therapy arm, experiencing ongoing clinical benefit, who experience a related AE where continuation of one of the drugs is considered, in the judgment of the treating

investigator AND overall PI, to be potentially life-threatening or with the potential for long-term harm to the patient, may be allowed to continue on the unrelated drug after discussion with the overall PI.

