5.10.4 Treatment Form

Purpose - Records the following information related to the time the participant receives protocol treatment:

- Participant, Protocol, Affiliate information
- Protocol treatment and supportive therapy per treatment cycle
- Protocol specific laboratory values per treatment cycle
- All medications other than protocol chemotherapy agents used to treat concomitant diagnoses, if applicable

Schedule for Submission – Submitted within 10 days after the last day of the cycle.

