7. SAFETY ASSESSMENTS AND TOXICITY MONITORING

All participants receiving investigational agents will be evaluated for safety. The safety parameters include all laboratory tests and hematological abnormalities, physical examination findings, and spontaneous reports of adverse events reported to the investigator by participants. All toxicities encountered during the study will be evaluated according to the NCI criteria assigned to the protocol and recorded prior to each course of therapy. This study will use the descriptions and grading scales found in the revised NCI Common Terminology Criteria for Adverse Events (CTCAE) version 4.0 will be utilized until March 31, 2018 for AE reporting. CTCAE version 5.0 will be utilized for AE reporting beginning April 1, 2018. All appropriate treatment areas should have access to a copy of the CTCAE version 5.0. A copy of the CTCAE version 5.0 can be downloaded from the CTEP web site http://ctep.cancer.gov/protocolDevelopment/electronic_applications/ctc.htm. Life-threatening toxicities should be reported immediately to the Protocol Chair and Institutional Review Board (IRB). Protocols using CTEP supplied agents should also report these toxicities via the CTEP-AERS system.

Additional safety assessments and toxicity monitoring will be outlined in the protocol.

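### The adverse-event definition in Section 11.2.1 leaves out some graded laboratory toxicity that the rest of the plan counts, so the Phase I and I-T toxicity tables may under-count it

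*Combined protocol and SAP*

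**What the plan says.** **The definition.** Section 11.2.1: "Abnormal laboratory values or diagnostic test results constitute adverse events only if they induce clinical signs or symptoms or require treatment"; the sentence then adds a need for more testing. There are three ways in: symptoms, treatment or extra testing. A value that takes none of them is not an AE.

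**The rules that act on laboratory values.**
- Section 5.3 (DLT): "Toxicity assessments will be done using NCI Common Terminology Criteria for Adverse Events (CTCAE v4.0". Its DLTs include Grade 4 neutropenia lasting at least four days and "All other hematologic toxicities of Grade 4", with no symptom condition. Grade 3 hypophosphatemia and hyponatremia are exempted by name.
- Section 6.3.1: a table whose title calls its contents hematologic adverse events acts on neutrophils, platelets and hemoglobin alone. Below the thresholds the instruction is "Hold treatment for up to 14 days until absolute neutrophil count" and the other two counts recover. Restarting at a lower dose is allowed, and patients without recovery by 14 days come off study.
- Section 6.1.1: the agent risk lists include falls in neutrophil and lymphocyte counts and rises in ALT, AST and creatinine.
- Appendix G, Section 7: "The safety parameters include all laboratory tests and hematological abnormalities", and all toxicities are to be graded by NCI criteria and recorded before each course.

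**Where the data go.** Non-serious AEs go on the toxicity forms (Section 11.5.2; Appendix G, 5.10.5). A separate Treatment Form holds "Protocol specific laboratory values per treatment cycle" (Appendix G, 5.10.4). Section 14.1.5 lists toxicity as a secondary endpoint for Phase I and I-T but not for Phase II. Section 14.3.1 says who is evaluable for toxicity, and names neither a data source nor a rule for grading laboratory values.

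**The concern.** The plan holds two standards for laboratory toxicity and does not say which one governs the tables. Section 11.2.1 asks what the abnormality led to; the other sections ask how abnormal the value was.

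The gap falls on a toxicity that the plan expects. Section 2.2.2 reports bone marrow as the target organ in olaparib toxicology. Section 5.4 says "Neupogen and other bone marrow-supportive agents, including erythropoiesis-stimulating agents, are not allowed during treatment", which narrows the treatment route by which an asymptomatic low count could qualify as an AE. The definition also leaves two practical questions open: whether withholding study drug is treatment, and whether a repeat count that the protocol already requires is a further diagnostic test. Two sites can answer differently for the same value.

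At stake are the laboratory toxicity rates for Phase I and I-T, and the adverse-event summaries that the DSMB may receive (Section 12.2).

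**Working it through.** **1. Which values can drop out.** Two kinds need to be separated.
- *Values that trigger no action.* Take a graded fall in lymphocytes without symptoms, untreated, and next checked at the routine visit. It is a listed term in 6.1.1 and a safety parameter in Appendix G, but 6.3.1 sets no lymphocyte threshold. Under 11.2.1 it is not an AE. Here the conflict is plain.
- *Values that trigger a hold or removal.* Restarting drug depends on recovered counts, so a repeat count is needed. If that repeat is a further test, 11.2.1 is met. If a required repeat is not, drug can be held for a value that is not an AE. The text allows both readings.

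**2. Count-based DLTs.** Section 5.3 applies CTCAE grades directly and does not refer to the 11.2.1 definition. Grade 4 counts that meet it are DLTs whatever form they appear on.

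**3. The 75% criterion.** Section 5.3 makes it a DLT if *AEs* related to treatment keep a patient from taking 75% or more of the planned Cycle 1 dose. Section 6.2 states the same criterion for *toxicity* related to drug. Inputs: a 28-day cycle (Section 5), and both drugs held together during DLT assessment (6.2). Fraction of dose taken after d days off = (28 − d)/28:

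| Days off | Fraction taken | Below 75%? |
|---|---|---|
| 7 | 21/28 = 75.0% | No |
| 8 | 20/28 = 71.4% | Yes |
| 14 | 14/28 = 50.0% | Yes |

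A hold of eight days or more for drug-related low counts that fall short of the Grade 4 criteria is a DLT under 6.2. Under 5.3 read with 11.2.1 it is a DLT only if the low count is an AE. This assumes that such a hold occurs in Cycle 1. Section 6.2 refers Phase I and I-T patients to 6.3.1 from Cycle 2 onward, and gives no length for a count-driven hold in Cycle 1.

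**4. The plan's escalation table (14.1.3).** With true DLT rate p and escalation on 0/3 or 1/6:

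P(escalate) = (1 − p)³ + 3p(1 − p)² × (1 − p)³

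- p = 0.30: 0.343 + 0.441 × 0.343 = 0.494 (plan: 0.49)
- p = 0.65: 0.0429 + 0.2389 × 0.0429 = 0.053 (plan: 0.053)

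All ten entries reproduce. The table takes the DLT rate as given and does not depend on 11.2.1.

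**5. Size of the under-count.** If a share s of laboratory events is asymptomatic, untreated and not further tested, then reported rate = true rate × (1 − s). The documents do not give s. For scale only, with an assumed true rate of 20% and an assumed s of 30% to 60%, the reported rate would be 0.20 × 0.70 = 14% down to 0.20 × 0.40 = 8%. Both inputs are assumptions, so this is not an estimate for this trial.

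**The case against.** The best defence is that the data are kept and only the label is uncertain. The Treatment Form collects laboratory values each cycle, Appendix G requires all toxicities to be graded and recorded, the DSMB can ask for laboratory values, and Section 11.1 counts laboratory tests among the ways an AE is detected. The values that matter most, those that stop treatment, need repeat counts and so probably pass 11.2.1. Section 5.4 bars growth factors and erythropoiesis-stimulating agents but otherwise leaves supportive care to best practice, so a low count may still be treated. In the first clinical study of olaparib, Section 6.1.2 reports anemia in 26%, neutropenia in 1% and thrombocytopenia in 5%, so low counts were not uniformly common.

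Most of this stands, and it limits the harm. It does not remove the conflict. Section 11.1 concerns AEs, which 11.2.1 then defines. Section 14.3.1 does not say that laboratory toxicity will be tabulated from Treatment Form values, so their presence there does not protect the tables.

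A reader might go further and infer three things that the documents do not support:
- *That 11.2.1 hides laboratory DLTs and so turns 2/6 into 1/6.* Section 5.3 defines the count-based DLTs by grade.
- *That an asymptomatic Grade 3 chemistry value might not count as a DLT event.* Exempting Grade 3 hypophosphatemia and hyponatremia by name makes sense only if laboratory grades otherwise count.
- *That Phase II toxicity rates, at 45 patients per arm, are a compromised endpoint.* Toxicity is not a listed Phase II endpoint, although the same definition would affect any Phase II AE table.

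**Conclusion.** The inconsistency is real and should be fixed before the toxicity tables are produced. As worded, Section 11.2.1 can keep asymptomatic graded laboratory toxicity that needs no treatment or extra test off the AE and toxicity forms, unevenly between sites. Laboratory toxicity in the Phase I and I-T AE tables may therefore be too low. The direction is clear if sites apply the definition literally; the size cannot be derived from the documents.

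For DLTs the exposure is confined to the 75% criterion. It matters only when a count-driven Cycle 1 hold of eight days or more occurs without another DLT. This is a should-fix matter of definition: no sample-size, power or escalation figure changes.

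**What to change.** 1. Amend Section 11.2.1 so that any Grade 3-4 laboratory value, and any laboratory value that leads to a hold, reduction or removal, is recorded as an AE whether or not it is symptomatic.
2. State in Section 14.3.1 that laboratory toxicity is graded from the values on the Treatment Form, not from AE entries alone. Check that the form takes mid-cycle and unscheduled results, since its description does not say.
3. Reconcile the wording of the 75% criterion in Sections 5.3 and 6.2 so that both use the same term. Which term to use is for the investigators to decide.

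The cost is a short amendment and some programmed grading of data already collected. Sites will enter somewhat more AEs, and reported laboratory toxicity rates may rise. Items 1 and 2 change no dose or treatment rule.

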11.2.2. Serious Adverse Event (SAE)

A serious adverse event is an undesirable sign, symptom, or medical condition which:

- is fatal or life-threatening;
- requires or prolongs inpatient hospitalization;

- results in persistent or significant disability/incapacity;
- constitutes a congenital anomaly or birth defect; or
- jeopardizes the participant and requires medical or surgical intervention to prevent one of the outcomes listed above.

Events **not** considered to be serious adverse events are hospitalizations for:

- routine treatment or monitoring of the studied indication, not associated with any deterioration in condition, or for elective procedures;
- elective or pre-planned treatment for a pre-existing condition that did not worsen;
- emergency outpatient treatment for an event not fulfilling the serious criteria outlined above and not resulting in inpatient admission;
- respite care.

11.2.3. Expectedness

Adverse events can be 'Expected' or 'Unexpected.'

Expected Adverse Event

Expected adverse events are those that have been previously identified as resulting from administration of the agent. For the purposes of this study, an adverse event is considered expected when it appears in the current adverse event list, the Investigator's Brochure, the package insert or is included in the informed consent document as a potential risk.

Refer to Section 6.1 for a listing of expected adverse events associated with the study agent(s).

Unexpected Adverse Event

For the purposes of this study, an adverse event is considered unexpected when it varies in nature, intensity or frequency from information provided in the current adverse event list, the Investigator's Brochure, the package insert or when it is not included in the informed consent document as a potential risk.

11.2.4. Attribution

Attribution is the relationship between an adverse event or serious adverse event and the study treatment. Attribution will be assigned as follows:

- Definite – The AE is clearly related to the study treatment.
- Probable – The AE is likely related to the study treatment.
- Possible – The AE may be related to the study treatment.
- Unlikely - The AE is doubtfully related to the study treatment.
- Unrelated - The AE is clearly NOT related to the study treatment.

11.3. Recording Adverse Events

Adverse event information will be obtained at each contact with the participant. All adverse events will be recorded on the appropriate study-specific case report forms (CRFs).

11.4. Reporting Adverse Events

Each adverse event will be assessed to determine if it meets the criteria for serious adverse event. If a serious adverse event occurs, expedited reporting will follow local policies, and federal guidelines and regulations as appropriate.

It is the responsibility of the participating investigator to notify the Principal Investigator (or Protocol Chair), IRB, and others of all serious adverse events as required in the protocol.

The Principal Investigator (or Protocol Chair) will provide information with respect to adverse events and safe use of the study treatment (e.g., safety reports, Action Letters) to all participating investigators as soon as the information becomes available.

11.5. Sponsor Notification by Investigator

Expedited AE reporting for this study must use CTEP-AERS (CTEP Adverse Event Reporting System), accessed via the CTEP home page (<http://ctep.cancer.gov>). The reporting procedures to be followed are presented in the “CTEP, NCI Guidelines: Adverse Event Reporting Requirements” which can be downloaded from the CTEP home page (<http://ctep.cancer.gov>). These requirements are briefly outlined in the tables below (Section 11.5.3).

In the rare event when Internet connectivity is disrupted a 24-hour notifications is to be made to NCI by telephone at: [contact], or [contact] for CIP studies. An electronic report MUST be submitted immediately upon re-establishment of internet connection. Please note that all paper CTEP-AERS forms have been removed from the CTEP website and will NO LONGER be accepted.

CTEP-AERS is programmed for automatic electronic distribution of reports to the following individuals: Study Coordinator of the Lead Organization, Principal Investigator, and the local treating physician. CTEP-AERS provides a copy feature for other e-mail recipients.

11.5.1. Expedited Reporting Guidelines

CTEP-AERS Reporting Requirements for Adverse Events That Occur Within 30 Days¹ of the Last Dose of the Investigational Agent on Phase 1 Trials

Phase 1 Trials								
	Grade 1	Grade 2	Grade 2	Grade 3		Grade 3		Grades 4 & 5 ²
	Unexpected and Expected	Unexpected	Expected	Unexpected with Hospitalization	Without Hospitalization	Expected with Hospitalization	without Hospitalization	Unexpected and Expected
Unrelated Unlikely	Not Required	Not Required	Not Required	10 Calendar Days	Not Required	10 Calendar Days	Not Required	24-Hour; 5 Calendar Days
Possible Probable Definite	Not Required	10 Calendar Days	Not Required	24-Hour; 5 Calendar Days	24-Hour; 5 Calendar Days	10 Calendar Days	Not Required	24-Hour; 5 Calendar Days
¹ Adverse events with attribution of possible, probable, or definite that occur greater than 30 days after the last dose of treatment with an agent under a CTEP IND require reporting as follows: CTEP-AERS 24-hour notification followed by complete report within 5 calendar days for: 
 • Grade 3 unexpected events with hospitalization or prolongation of hospitalization • Grade 4 unexpected events • Grade 5 expected events and unexpected events ² Although an CTEP-AERS 24-hour notification is not required for death clearly related to progressive disease, a full report is required as outlined in the table.								
December 15, 2004								

Phase 2 and 3 Trials									
	Grade 1	Grade 2	Grade 2	Grade 3		Grade 3		Grades 4 & 5 ²	Grades 4 & 5 ²
	Unexpected and Expected	Unexpected	Expected	Unexpected with Hospitalization	Without Hospitalization	Expected with Hospitalization	without Hospitalization	Unexpected	Expected
Unrelated Unlikely	Not Required	Not Required	Not Required	10 Calendar Days	Not Required	10 Calendar Days	Not Required	10 Calendar Days	10 Calendar Days
Possible Probable Definite	Not Required	10 Calendar Days	Not Required	10 Calendar Days	10 Calendar Days	10 Calendar Days	Not Required	24-Hour; 5 Calendar Days	10 Calendar Days
¹ Adverse events with attribution of possible, probable, or definite that occur greater than 30 days after the last dose of treatment with an agent under a CTEP IND require reporting as follows: CTEP-AERS 24-hour notification followed by complete report within 5 calendar days for: 
 • Grade 4 and Grade 5 unexpected events CTEP-AERS 10 calendar day report: 
 • Grade 3 unexpected events with hospitalization or prolongation of hospitalization • Grade 5 expected events ² Although an CTEP-AERS 24-hour notification is not required for death clearly related to progressive disease, a full report is required as outlined in the table.									
December 15, 2004									

Note: All deaths on study require both routine and expedited reporting regardless of causality. Attribution to treatment or other cause must be provided.

- Expedited AE reporting timelines defined:
 - “24 hours; 5 calendar days” – The investigator must initially report the AE via CTEP-AERS within 24 hours of learning of the event followed by a complete CTEP-AERS report within 5 calendar days of the initial 24-hour report.

- “10 calendar days” - A complete CTEP-AERS report on the AE must be submitted within 10 calendar days of the investigator learning of the event.
- Any medical event equivalent to CTCAE grade 3, 4, or 5 that precipitates hospitalization (or prolongation of existing hospitalization) must be reported regardless of attribution and designation as expected or unexpected with the exception of any events identified as protocol-specific expedited adverse event reporting exclusions.
- Any event that results in persistent or significant disabilities/incapacities, congenital anomalies, or birth defects must be reported via CTEP-AERS if the event occurs following treatment with an agent under a CTEP IND.
- Use the NCI protocol number and the protocol-specific patient ID assigned during trial registration on all reports.

